### 7.2.1.2 Radiology procedure

To ensure a valid comparison of tumor data and uniformity in the assessment of tumor response during the study, the following procedure must be implemented at the study center:

- All lesions identified at screening (target and non-target) will be reassessed using the same method (CT scan with contrast or MRI with contrast etc.) and technique (i.e. for scans, the use of contrast, slice thickness etc.) throughout the course of the study so that the basis of measurement remains consistent for accurate comparison and determination of disease status.
- Regarding the use of contrast, at screening (≤ 4 weeks prior to randomization), all patients should have a CT scan with contrast or MRI with contrast of the chest, abdominal and pelvic area. CT scan without contrast or MRI without contrast may be used for patients who are allergic/sensitive to the radiographic contrast media used in CT scans or MRI. Ultrasound scans cannot be used to measure tumor lesions.
- All CT scans and MRIs obtained on all patients enrolled at the center should be reviewed by the local radiologist who together with the investigator will determine the local assessment of response and progression. The same radiologist/physician should perform the evaluation for the entire duration of the study if possible. All radiology evaluations will be performed by the local radiologist. All bone scans and bone imaging (X-ray, CT or MRI) obtained from the patient with bone metastases at baseline also should be reviewed similarly.

## 7.2.2 Safety and tolerability assessments

Safety assessments will consist of monitoring and recording all adverse events (AEs), including serious adverse events (SAEs), the regular monitoring of hematology, serum chemistry, coagulation, urinalysis, routine monitoring of vital signs (heart rate, blood pressure, and body temperature), weight, ECOG performance status, CT scans of the chest, abdominal, and pelvic area, physical examinations, cardiac assessments (MUGA scan/ECHO), ECG and pulmonary function tests (PFTs) if clinically indicated.

These assessments should be performed  $\pm$  7 days of the scheduled day of assessment (Table 7-1) except for adverse events and concomitant medications that will be evaluated and recorded continuously throughout the study.

Significant findings of any safety evaluation must be recorded either on the Relevant Medical History/Current Medical Conditions eCRF (if present before signing informed consent) or on the Adverse Events eCRF (if newly occurring or worsening since signing informed consent).

### 7.2.2.1 Adverse events

An adverse event for the purposes of this protocol is the appearance of (or worsening of any pre-existing) undesirable sign(s), symptom(s), or medical condition(s) occurring after signing the informed consent even if the event is not considered to be related to the study drug(s). Please refer to Section 6.1 for the protocol-specific definitions of study drug and study treatment.

Adverse events will be assessed according to the NCI Common Terminology Criteria for Adverse Events (CTCAE) version 4.0. If CTCAE grading does not exist for an adverse event, the severity of mild, moderate, severe, and life-threatening, or grades 1 - 4, will be used. CTCAE grade 5 (death) will not be used in this study; rather, death information will be collected on a separate eCRF page. Adverse event monitoring should be continued for at least 30 days following the last dose of study treatment.

Adverse events that begin or worsen after informed consent should be recorded in the Adverse Events CRF. Conditions that were already present at the time of informed consent should be recorded in the Medical History page of the patient's CRF. Abnormal laboratory values or test results constitute adverse events only if they induce clinical signs or symptoms, or require therapy (e.g., any hematologic abnormality that requires transfusion or cytokine treatment); and should be recorded on the Adverse Events eCRF under the signs, symptoms or diagnosis associated with them. In addition, isolated abnormal laboratory values that cause study discontinuation or constitutes in and of itself a Serious Adverse Event should be recorded on the Adverse Events eCRF

The occurrence of adverse events should be sought by non-directive questioning of the patient at each visit during the study. Adverse events also may be detected when they are volunteered by the patient during or between visits or through physical examination, laboratory test, or other assessments. As far as possible, each adverse event should be evaluated to determine:

- 1. The severity grade CTCAE grade 1-4
- 2. Its relationship to each study drug (suspected/not suspected)
- 3. Its duration (start and end dates or if continuing at final exam)
- 4. Action taken (no action taken; study drug dosage adjusted/temporarily interrupted; study drug permanently discontinued due to this adverse event; concomitant medication taken; non-drug therapy given; hospitalization/prolonged hospitalization)
- 5. Whether it is serious, where a serious adverse event (SAE) is defined as one which:
  - Is fatal or life-threatening
  - Results in persistent or significant disability/incapacity
  - Constitutes a congenital anomaly/birth defect
  - Requires inpatient hospitalization or prolongation of existing hospitalization, unless hospitalization is for:
    - Routine treatment or monitoring of the studied indication, not associated with any deterioration in condition (specify what this includes)
    - Elective or pre-planned treatment for a pre-existing condition that is unrelated to the indication under study and has not worsened since signing the informed consent
    - Treatment on an emergency outpatient basis for an event not fulfilling any of the definitions of a SAE given above and not resulting in hospital admission
    - Social reasons and respite care in the absence of any deterioration in the patient's general condition
  - Is medically significant, i.e., defined as an event that jeopardizes the patient or may require medical or surgical intervention to prevent one of the outcomes listed above

# Unlike routine safety assessments, SAEs are monitored continuously and have special reporting requirements; see Section 8.1.

All adverse events should be treated appropriately. Such treatment may include changes in study drug treatment including possible interruption or discontinuation, starting or stopping concomitant treatments, changes in the frequency or nature of assessments, hospitalization, or any other medically required intervention. Once an adverse event is detected, it should be followed until its resolution, an assessment should be made at each visit (or more frequently, if necessary) of any changes in its severity, its suspected relationship to the study drug(s), any of the interventions required to treat it, and its outcome.

Information about common side effects already known about the investigational drug can be found in the [Investigator's Brochure] or will be communicated between IB updates in the form of Investigator Notifications. This information will be included in the patient informed consent and should be discussed with the patient during the study as needed.

### 7.2.2.2 Physical examination, weight and height

Physical examination must include a total body examination (i.e., general appearance, skin, neck, including thyroid, eyes, ears, nose, throat, lungs, heart, abdomen, back, lymph nodes and extremities) and a clinical neurological examination.

Physical examination and weight check will be performed at the following visits:

- Baseline ( $\leq 7$  days prior to administration of the study drugs)
- Day 1 (prior to administration of the study drugs);
- Week 3, week 6 and then every 6 weeks
- End of Treatment

Height is measured only at Baseline visit.

Significant findings that are present prior to informed consent must be included in the Relevant Medical History / Current Medical Conditions eCRF. Significant findings made after the start of study drug which meet the definition of an adverse event must be recorded on the Adverse Event eCRF.

#### 7.2.2.3 Vital signs

Body temperature, respiration rate, sitting pulse rate and sitting blood pressure will be routinely measured.

- Baseline ( $\leq 7$  days prior to administration of the study drugs)
- Day 1 (prior to administration of the study drugs)
- Week 3, week 6, and every 6 weeks
- End of Treatment

#### 7.2.2.4 Performance status

The ECOG performance status Scale Index allows patients to be classified as to their functional impairment, the definition of scores in relation to the PS is given in Table 7-2.

ECOG PS will be evaluated at the following visits:

- Baseline ( $\leq 7$  days prior to administration of the study drugs)
- Day 1 (prior to administration of the study drugs)
- Every 6 weeks
- End of treatment

Table 7-3 ECOG Performance Status Scale

Score	Performance Status
0	Fully active, able to carry on all pre-disease performance without restriction.
1	Restricted in physically strenuous activity but ambulatory and able to carry out work of a light or sedentary nature, e.g., light housework, office work.
2	Ambulatory and capable of all self-care but unable to carry out any work activities. Up and about more than 50% of waking hours.
3	Capable of only limited self-care, confined to bed or chair more than 50% of waking hours.
4	Completely disabled. Cannot carry on any self-care. Totally confined to bed or chair.
5	Dead

#### 7.2.2.5 Management of Hepatitis reactivation/flare

## Monitoring and prophylactic treatment for hepatitis B reactivation

Table 7-4 provides details of monitoring and prophylactic therapy according to the screening results of viral load and serologic markers testing. If the patient is already known to have a chronic infection with HBV and is taking anti-HBV medication, the site does not have to wait for the screening HBV results from the central laboratory prior to randomization.

Table 7-4 Action to be taken based on Hepatitis B Screening Results

	Result	Result	Result	Result	Result
HBV-DNA + + or -		-	-	-	
HBsAg	+ or -	+	-	-	-
HBs Ab	+ or -	+ or -	+ and no prior HBV vaccination	+ or -	- or + with prior HBV vaccination
HBc Ab + or - + or -		+ or -	+	-	
Recommendation	Prophylaxis treatment should be started 1-2 weeks prior to first dose of study drug.  Monitor HBV-DNA approximately every 6 weeks (from Visit 3 and onwards)		No prophylaxis  Monitor HBV-DNA approximately every 6 weeks (from Visit 3 and onwards)		No specific action

Antiviral prophylaxis therapy should continue for at least 4 weeks after last dose of study drug. For hepatitis B reactivation, definition and management guidelines see Table 7-5.

Table 7-5 Guidelines for management of hepatitis B

HBV reactivation (with or without clinical signs and symptoms)*		
For patients with baseline results: Positive HBV-DNA OR Positive HBsAg	Treat: Start a second antiviral AND Interrupt study drug administration until resolution: - ≤ baseline HBV-DNA levels	
Reactivation is defined as: [Increase of 1 log in HBV-DNA relative to baseline HBV-DNA value OR new appearance of measurable HBV-DNA]	If resolution occurs within 28 days, study drug should be re-started at one dose lower, if available. (see Table 6-4- Study drug dose reductions) If the patient is already receiving the lowest dose of study drug according to the protocol, the patient should restart at the same dose after resolution. Both antiviral therapies should continue at least 4 weeks after last dose of study drug.  If resolution occurs > 28 days, patients should discontinue study drug but continue both antiviral therapies at least 4 weeks after last dose of study drug.	

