### 6.2.1.1 Everolimus

Management of severe or intolerable adverse reactions may require temporary dose reduction and/or interruption of everolimus therapy. If dose reduction is required, the suggested dose is approximately 50% lower than the daily dose previously administered.

If a patient already had 2 levels of dose reduction, no further dose reduction is permitted.

Patients who interrupt study treatment for more than 4 weeks must discontinue from the study or the study medication (in combination arm if applicable).

Recommendations for dose reduction, interruption or discontinuation of everolimus in the management of adverse reactions are summarized in Table 6-4, Table 6-5 and Table 6-6.

Table 6-4 Recommendation of everolimus dose reductions

Dose level	Dose and schedule	
0 = starting dose 10 mg	10 mg daily (2 × 5 mg daily)	
-1 dose level	5 mg daily	
-2 dose level	5 mg every other day	

Table 6-5 Everolimus dose adjustment and management recommendation for adverse reactions

	auverse reactions						
Adverse Drug Reaction	Severity a	Everolimus Dose Adjustment b and Management Recommendations					
Non-infectious pneumonitis	Grade 1 Asymptomatic, radiographic findings only	No dose adjustment required. Initiate appropriate monitoring.					
	Grade 2 Symptomatic, not interfering with ADL c	Consider interruption of therapy, rule out infection and consider treatment with corticosteroids until symptoms improve to $\leq$ grade 1.					
		Re-initiate everolimus at a lower dose.					
		Discontinue treatment if failure to recover within 4 wks.					
	Grade 3 Symptomatic,	Interrupt everolimus until symptoms resolve to $\leq$ grade1.					
	interfering with ADL c ; O 2 indicated	Rule out infection, and consider treatment with corticosteroids.					
		Consider re-initiating everolimus at a lower dose. If toxicity recurs at grade 3, consider discontinuation.					
	Grade 4 Life-threatening, ventilatory support indicated	Discontinue everolimus, rule out infection, and consider treatment with corticosteroids.					
Stomatitis	Grade 1	No dose adjustment required.					
	Minimal symptoms, normal diet	Manage with non-alcoholic or salt water (0.9%) mouth wash several times a day.					
	Grade 2	Temporary dose interruption until recovery to grade $\leq 1$ .					
	Symptomatic but can eat and swallow modified diet	Re-initiate everolimus at the same dose.					

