		If stomatitis recurs at grade 2, interrupt dose until recovery to grade $\leq$ 1. Re-initiate everolimus at a lower dose.					
		Manage with topical analgesic mouth treatments (e.g. benzocaine, butyl aminobenzoate, tetracaine hydrochloride, menthol or phenol) with or without topical corticosteroids (i.e. triamcinolone oral paste).					
	Grade 3	Temporary dose interruption until recovery to grade $\leq 1$ .					
	Symptomatic and unable to adequately eat or hydrate orally	Re-initiate everolimus at a lower dose.					
	, 2.2.2 2.2,	Manage with topical analgesic mouth treatments (i.e. benzocaine, butyl aminobenzoate, tetracaine hydrochloride, menthol or phenol) with or without topical corticosteroids (i.e. triamcinolone oral paste).d					
	Grade 4 Symptoms associated with life-threatening consequences	Discontinue everolimus and treat with appropriate medical therapy.					

Adverse Drug Reaction	Severity a	Everolimus Dose Adjustment b and Management Recommendations							
Other non- hematologic	Grade 1	If toxicity is tolerable, no dose adjustment required.							
toxicities		Initiate appropriate medical therapy and monitor.							
(excluding metabolic events)	Grade 2	If toxicity is tolerable, no dose adjustment required.							
		Initiate appropriate medical therapy and monitor.							
		If toxicity becomes intolerable, temporary dose interruption until recovery to grade $\leq 1$ . Re-initiate everolimus at the same dose.							
		If toxicity recurs at grade 2, interrupt everolimus until recovery to grade ≤1. Re-initiate everolimus at a lower dose.							
	Grade 3	Temporary dose interruption until recovery to grade $\leq 1$ .							
		Initiate appropriate medical therapy and monitor.							
		Consider re-initiating everolimus at a lower dose. If toxicity recurs at grade 3, consider discontinuation.							
	Grade 4	Discontinue everolimus and treat with appropriate medical therapy.							
Metabolic events	Grade 1	No dose adjustment required.							
(e.g. hyperglycemia,		Initiate appropriate medical therapy and monitor.							
dyslipidemia)	Grade 2	No dose adjustment required.							
		Manage with appropriate medical therapy and monitor.							
	Grade 3 Temporary dose interruption.								
		Re-initiate Afinitor at a lower dose.							
		Manage with appropriate medical therapy and monitor.							
	Grade 4	Discontinue everolimus and treat with appropriate medical therapy.							

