#### Table 7-6 Guidelines for management of hepatitis C flare

HCV flare *	
For patients with baseline results: Detectable HCV-RNA,	Discontinue study drug
HCV flare is defined as: > 2 log10IU/mL increase in HCV-RNA AND ALT elevation > 5 x ULN OR 3 x baseline level, whichever is higher	
For patients with baseline results: Knowledge of past hepatitis C infection with no detectable HCV-RNA, HCV flare is defined as: New appearance of detectable HCV-RNA AND ALT elevation > 5 x ULN OR 3 x baseline level, whichever is higher	Discontinue study drug

\*All flares of hepatitis C are to be recorded as grade 3 (CTCAE v 4.0 Metabolic Laboratory/Other: Viral Flare), unless considered life threatening by the investigator; in which case they should be recorded as grade 4 (CTCAE v 4.0 Metabolic Laboratory/Other: Viral Re-activation). Date of viral flare is the date on which both the clinical criteria described above were met (e.g., for a patient whose HCV-RNA increased by 2 logs on 01 JAN 2011 and whose ALT reached > 5 x ULN on 22 JAN 2011), the date of viral flare is 22 JAN 2011.

\* All reactivations of hepatitis B are to be recorded as grade 3 (CTCAE v4.0 Metabolic Laboratory/Other: Viral Reactivation), unless considered life threatening by the investigator; in which case they should be recorded as grade 4 (CTCAE v4.0 Metabolic Laboratory/Other: Viral Re-activation). Date of viral reactivation is the date on which the rise or reappearance of HBV- DNA was recorded.

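### For everolimus, a grade 4 hepatitis B reactivation that resolves within 28 days is restarted under Table 7-5 but discontinued under Table 6-5, with no written precedence; Table 7-5 also cites the wrong dose table for some patients

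*Protocol*

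**What the plan says.** **Hepatitis B rules.** Protocol section 7.2.2.5 directs sites: "For hepatitis B reactivation, definition and management guidelines see Table 7-5". Table 7-5 has two rows, defined by baseline serology. Both cover symptomatic and asymptomatic reactivations, and both require an antiviral (a second one in row 1, a first one in row 2) and an interruption of study drug. Resolution means HBV-DNA back to baseline or below in row 1, and undetectable in row 2. Then, in both rows: "If resolution occurs within 28 days, study drug should be re-started at one dose lower, if available". A patient already at the lowest dose restarts at that dose. If resolution takes longer than 28 days, study drug is discontinued. The hepatitis B footnote records every reactivation as grade 3 "unless considered life threatening by the investigator; in which case they should be recorded as grade 4" (the hepatitis C footnote uses the same words).

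**General everolimus rules.** Section 6.2.1.1 says that recommendations for reduction, interruption or "discontinuation of everolimus in the management of adverse reactions are summarized in Table 6-4, Table 6-5 and Table 6-6". In Table 6-5, the grade 4 entry for other non-hematologic toxicities and for metabolic events is the same: "Discontinue everolimus and treat with appropriate medical therapy". At grade 3, the other non-hematologic row prescribes "Temporary dose interruption until recovery to grade" 1 or lower, followed by "Consider re-initiating everolimus at a lower dose. If toxicity recurs at grade 3, consider discontinuation".

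**Laboratory values.** Section 7.2.2.6 sends dose modification for abnormal laboratory values to Tables 6-4 to 6-7. Its own Table 7-7 lists HBV-DNA among the study tests. Table 7-5 is not mentioned there.

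**The concern.** A reactivation that the investigator judges life threatening is foreseen inside Table 7-5, yet the grade changes nothing in that table's action. The general table gives the opposite instruction at that grade. Two sites with the same patient on everolimus could each follow the protocol, one restarting the drug and the other stopping it.

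The stake is patient safety. Table 7-5 defines resolution by viral load alone, whereas the grade 3 other non-hematologic row of Table 6-5 waits for the toxicity itself to recover. Read literally, Table 7-5 could permit a restart on HBV-DNA before clinical recovery from a life-threatening event.

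The second problem is a plain drafting error in operative dosing text. Table 7-5 tells sites to restart one dose lower, and in some arm and row combinations it then points them to a table that does not contain the drug's dose levels.

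**Working it through.** There is no plan figure to reproduce and no formula applies. The check sets the instructions side by side.

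**1. Does Table 6-5 reach a hepatitis B reactivation?** It does not name hepatitis, so it can apply only through a general row. The two candidates are other non-hematologic toxicities and, because the footnote files the event under a metabolic/laboratory heading, metabolic events. Both say discontinue at grade 4, so the classification does not matter. Sections 6.2.1.1 and 7.2.2.6 lead to the table with no hepatitis exception.

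**2. Everolimus, resolved within 28 days, grade 4.** Dose levels are from Table 6-4.

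| Dose before | Table 7-5 | Table 6-5 |
|---|---|---|
| 10 mg daily | restart at 5 mg daily | discontinue |
| 5 mg daily | restart at 5 mg every other day | discontinue |
| 5 mg every other day | restart unchanged | discontinue |

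The actions are opposite at every dose level.

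**3. Grade 3, resolved within 28 days.** At the two upper dose levels, Table 7-5 restarts one level lower and Table 6-5 interrupts and then allows or directs a lower dose. These are compatible.

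**4. Resolution after more than 28 days.** Table 7-5 discontinues. Section 6.2.1.1 discontinues after an interruption of more than 4 weeks (4 × 7 = 28 days). These agree. The conflict is therefore confined to grade 4 with resolution inside 28 days.

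**5. Is there a precedence rule?** Sections 4.1.1 (hepatitis B screening), 7.1.1.3 and 7.2.2.5 point to the hepatitis guidance. Sections 6.2.1.1 and 7.2.2.6 point to the general tables. No sentence ranks them.

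**6. Dose-table pointers in Table 7-5.**

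| Row (baseline serology) | Table cited | Patients left without dose levels |
|---|---|---|
| 1: HBV-DNA or HBsAg positive | 6-4 (everolimus) | capecitabine arm |
| 2: both negative, with HBc Ab positive or HBs Ab positive without vaccination | 6-7 (capecitabine) | both everolimus arms |

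Serology does not depend on the randomized arm, so patients from any arm can fall in either row.

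**The case against.** The strongest reply is that the specific table governs the general one. Three sections send hepatitis B to its own guidance, and Table 6-5 applies only through residual rows. The absence of a grade split may also be deliberate. The footnote foresees grade 4 and still leaves the action alone, and Table 7-6 likewise has a single action for hepatitis C flares (stop), whatever the grade. This largely stands: Table 7-5 is the more natural rule. It remains an inference, and section 7.2.2.6 cuts against it by routing abnormal laboratory values, HBV-DNA among the listed tests, to the general tables.

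A second reply is that discontinuing need not be permanent. Section 6.2.1 uses the word for a hold that becomes permanent only after 4 weeks, and Tables 6-6 and 6-7 add a word for permanence that Table 6-5 lacks at grade 4. This has some force, and the definition in section 7.1.3.1 does not settle it because it concerns withdrawal from the whole study treatment. Within Table 6-5, however, grade 3 is worded as an interruption with re-initiation and grade 4 has no route back, so a stop is the better reading.

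A reader might also infer wider disagreement, at the lowest everolimus dose and for capecitabine. The documents do not support that:

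- At the lowest everolimus dose, section 6.2.1.1 says "If a patient already had 2 levels of dose reduction, no further dose reduction is permitted". The grade 3 other non-hematologic entry only asks the site to consider a lower dose. Table 7-5's same-dose restart fills a gap more than it contradicts an order.
- For capecitabine, section 6.2.1.2 lets the local label be used in place of Table 6-7, and Table 7-5 does not define what one dose lower means for that drug.

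**Conclusion.** The point holds as a minor drafting inconsistency in safety instructions. It has two parts: opposite stated actions for one rare everolimus situation with no written precedence, and dose-table pointers that fail for some patients in each row.

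A reader might infer that sites are compelled to re-treat after a life-threatening reactivation. They are not: sections 6.1.3 and 7.1.3.2 let the investigator stop treatment, and both tables are framed as recommendations or guidelines. Nor is a site left with no basis for choosing, since Table 7-5 is the natural first reference.

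The number of patients affected cannot be computed, because the documents give no reactivation rate. It should be small, and at Amendment 3 only 11 of 309 patients were still on treatment, across all arms. Sample size is unaffected. The hazard ratio analysis is also unaffected: it is by randomized arm, and SAP section 3.8.1 does not censor PFS at treatment discontinuation.

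The conflict rests on reading the grade 4 entry of Table 6-5 as a stop and on the general rows reaching hepatitis B. The pointer error rests on neither.

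**What to change.** 1. In both rows of Table 7-5, cite Table 6-4 for everolimus and Table 6-7 or the local label for capecitabine.
2. State in Table 7-5 that it governs hepatitis B reactivation, with a cross-reference from Table 6-5 and section 7.2.2.6.
3. State the grade 4 action explicitly. Discontinuing everolimus is the safer default and matches Table 6-5. If the sponsor's clinicians intend a restart after a resolved grade 4 reactivation, the table should say so. That is a clinical decision, and the text only needs to record it.

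The cost is two sentences, two corrected pointers and two cross-references. The downside of the default is that a rare patient whose grade 4 reactivation has resolved may lose everolimus re-treatment; in the combination arm, section 7.1.3.1 allows exemestane to continue. No data collection or analysis changes.
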